## **10.4 Analysis of Vital Signs**

Vital sign measurements of systolic and diastolic blood pressure, pulse rate, and body temperature will be summarized.

Each vital sign variable will be summarized for all time points (starting with Baseline) with the number of non-missing observations, mean and standard deviation, median, minimum and maximum. Mean change from Baseline to each applicable post-baseline visit in both Periods 1 and 2 will be summarized for each vital sign variable, with the

number of observations, Baseline mean, and visit mean. The change from Baseline mean, standard error, and 95% confidence interval will be presented for the mean change from Baseline by treatment group in Period 1 and Period 2.

Vital sign variables will be evaluated based on potentially clinically important (PCI) criteria ([Appendix C](#)) in Period 1 and for the ALL UPA Population. For each vital signs PCI criterion, the number and percentage of subjects who have at least one vital sign value meeting the criteria will be summarized. Listings will be provided to summarize subject-level vital sign data for subjects meeting PCI criteria.

### **10.5 Other Safety Analyses**

Not applicable.

### **10.6 Safety Subgroup Analyses**

Selected safety summary will be provided for adolescent subgroup, i.e., TEAE overview; TEAE, SAE and death by SOC and PT; and AESI.

### **11.0 Other Analyses**

Not applicable.

### **12.0 Interim Analyses**

There will be no interim analyses.

### **12.1 Data Monitoring Committee**

Given that the study is only assessor blinded and no subjects participating in the study will receive placebo, the causality of any AEs reported in the participants can be adequately assessed in the context of upadacitinib or dupilumab treatment. The study team will monitor and evaluate any AEs to identify findings that could put the study participants at risk and then make clinical decisions regarding the study conduct, which could include modification or termination of the study. This can adequately safeguard the

participants. Given the above, it is not necessary to implement an independent Drug Monitoring Committee for the conduct of this study.

### 13.0 Overall Type-I Error Control

The statistical comparisons of upadacitinib versus dupilumab for the primary efficacy endpoint and the ranked secondary endpoints will be carried out in the hierarchical order under a 2-sided significance level of 0.05. This means that statistically significant results for the comparison in the higher rank (primary, then ranked secondary endpoints) are necessary to initiate the testing of the next comparison in the lower rank. Since a step-down procedure is used, each comparison will be tested at a significance level of 0.05 and the family-wise error rate is strongly controlled at 0.05.

### 14.0 Version History

**Table 5. SAP Version History Summary**

Version	Date	Summary
1.0	26 January 2023	Initial version
2.0	26 July 2023	Exclude significant non-compliance site of the study
3.0	13 March 2024	Changes to keep consistent with Protocol V2.0: 
 
• Updated Age strata to "Age <64" throughout the text.
 
• Removed "Other Event of Interest content" in Section 3.4, Section 10.2.2, Section 10.2.3, Section 10.2.4.
 
• Added contents about "Other Safety Topics of Interest" in Section 3.4, Section 10.2.2, Section 10.2.4.
 
• Updated Definition of Additional Safety Topics in Appendix F.
 
• Added clarification about follow-up visit in Section 2.2.
 
• Added clarification about compliance in Section 6.0.
 
 Changes for clarification/typos: 
 
• Added clarification for duration of upadacitinib 15 mg in Section 6.0.
 

[figure not shown]
Version	Date	Summary
		
 
• Added clarification of AESI list in Section 10.2.3, Section 10.2.4, Section 10.2.6.
 
• Added the footnote about random seeds in Appendix C.
 
• Removed "acne adverse events" content in Section 10.2.3.
 
• Removed Covid-19 in AE summary in Section 10.2.2.
 
• Added nQuery version in Section 2.4.
 
• Added clarification about the additional objective related to Study Period 2 in Section 2.1.
 
• Added clarification about Safety Subgroup analyses in Section 10.6.
 

4.0	11 April 2024	
 
• Added superscripts in Table A to match the corresponding footnotes in Appendix D.
 
• Added clarification in Section 9.1 when deriving actual stratum: "During derivation, any subject not already within the current strata will be included in the nearest stratum."
 
• Added supplementary analysis for primary and ranked secondary endpoints by excluding the subjects whose efficacy assessments for primary and ranked secondary endpoints evaluations were not completed by blinded efficacy assessors or were completed by blinded efficacy assessors who were accidentally unblinded to treatment group information, in Section 9.3.3 and Section 9.4.3.
 
• Moved Breslow-Day test statement from Section 9.3.2 to Section 9.6.
 
• Clarification language in Section 10.2.3, Section 10.2.4, Section 10.2.6 regarding AESIs which were moved to Appendix B Definition of Adverse Events of Special Interest.
 

## Appendix B. Definition of Adverse Events of Special Interest

AEs of Special Interest (AESI) will be identified by the following CMQ, SMQ, and other search criteria (**Note:** for each database lock, the categories of AESIs will follow the latest version of Product Safety Statistical Analysis Plan for Upadacitinib, with the exceptions of Hepatitis B Reactivation which is not an AESI. AESIs with the corresponding code for the MedDRA version in that DBL will be shown in a summary table):

AESI	Type of MedDRA Query	Broad or Narrow Search	SMQ/CMQ Search Criteria
Serious Infections	CMQ		"Infections" - Subset for SAEs
Opportunistic Infections excluding tuberculosis and herpes zoster	CMQ		"Opportunistic Infection excluding tuberculosis and herpes zoster"
Possible Malignancy	SMQ	Narrow	"Malignancies"
Malignancy	SMQ		"Malignant Tumours"
Non-Melanoma Skin Cancer (NMSC)	SMQ/CMQ	SMQ Narrow	Skin Malignant tumours (Narrow SMQ) removing Melanoma CMQ
Malignancy excluding NMSC			Malignancy Narrow SMQ and removing NMSC output
Lymphoma	SMQ		"Malignant Lymphomas"
Hepatic Disorder (including DILI events)	SMQ	Narrow	"Drug Related Hepatic Disorders"
Adjudicated Gastrointestinal Perforations	Medical review of events identified by the "Gastrointestinal Perforation" SMQ Narrow search		
Anemia	CMQ		"Non-Hemolytic and Non-Aplastic Anemias"
Neutropenia	CMQ		"Hematological Toxicity - Neutropenia"
Lymphopenia	CMQ		"Hematological Toxicity - Lymphopenia (Veliparib Product Specific)"
Herpes Zoster	CMQ		"Herpes Zoster"

AESI	Type of MedDRA Query	Broad or Narrow Search	SMQ/CMQ Search Criteria
Renal Dysfunction	SMQ	Narrow	"Acute Renal Failure"
Active Tuberculosis	CMQ		"Active Tuberculosis"
Creatine Phosphokinase (CPK) Elevations and Rhabdomyolysis	PT		PT of "Blood creatine phosphokinase increased"; PT of "Rhabdomyolysis"
Adjudicated cardiovascular events a	Output from CAC		
MACE*			
Cardiovascular Death			
Non-fatal Myocardial Infarction			
Non-fatal Stroke			
Other Adjudicated Cardiovascular Events			
Undetermined/Unknown Cause of Deaths			
Adjudicated Thrombotic Events	Output from CAC		
VTE**			
Deep Vein Thrombosis			
Pulmonary Embolism			
Other Venous Thrombosis			
Arterial Thromboembolic Events (non-cardiac, non-neurologic)			

CAC Cardiovascular Adjudication Committee; CMQ company MedDRA query; PT preferred term; SMQ standard MedDRA query

\* MACE: Major Adverse Cardiovascular Events, defined as cardiovascular death, non fatal myocardial infarction and non fatal stroke.

\*\* VTE: Venous thromboembolic events, defined as deep vein thrombosis (DVT) and pulmonary embolism (PE) (fatal and non fatal).

a. Reviewed and adjudicated by an independent Cardiovascular Adjudication Committee in a blinded manner.

## Appendix C. Potentially Clinically Important Criteria for Safety Endpoints

The criteria for Potentially Clinically Important (PCI) laboratory findings are described in Table C-1 and Table C-2, PCI criteria for the liver function tests are described in Table C-3, and the PCI criteria for vital sign findings are described in Table C-4.

**Table C-1. Criteria for Potentially Clinically Important Hematology Values**

Hematology Variables	Units	Definition of Potentially Clinically Important
		Very Low
Hemoglobin	g/dL	< 8.0
Platelets count	10  /L	< 50.0
WBC count	10  /L	< 2.0
Neutrophils	10  /L	< 1.0
Lymphocytes	10  /L	< 0.5

**Table C-2. Criteria for Potentially Clinically Important Chemistry Values**

Chemistry Variables	Units	Definition of Potentially Clinically Important	
		Very Low	Very High
ALP	U/L		> 5.0 × ULN
SGOT/AST	U/L		> 5.0 × ULN
SGPT/ALT	U/L		> 5.0 × ULN
Albumin	g/L	< 20	
Glucose	mmol/L	< 2.2	> 13.9
Triglycerides	mmol/L		> 5.7
Creatinine	mcmol/L		> 3.0 × ULN
Potassium	mmol/L	< 3.0	> 6.0
Calcium	mmol/L	< 1.75	> 3.1
Sodium	mmol/L	< 130	> 155
Phosphate	mmol/L	< 0.6	
CPK	U/L		> 5.0 × ULN
Total Cholesterol	mmol/L		> 10.34

**Table C-3. Criteria for Potentially Clinically Important Liver Function Tests**

Variables	Units	Definition of Potentially Clinically Important
		Very High
AST	U/L	$\geq 3 \times \text{ULN}$ $\geq 5 \times \text{ULN}$ $\geq 10 \times \text{ULN}$ $\geq 20 \times \text{ULN}$
ALT	U/L	$\geq 3 \times \text{ULN}$ $\geq 5 \times \text{ULN}$ $\geq 10 \times \text{ULN}$ $\geq 20 \times \text{ULN}$
Total Bilirubin	UMOL/L	$\geq 2 \times \text{ULN}$
Alkaline phosphatase	U/L	$\geq 1.5 \times \text{ULN}$
ALT (U/L) and/or AST (U/L) and concurrent TBL (UMOL/L)		ALT and/or AST $\geq 3 \times \text{ULN}$ and concurrent TBL $\geq 1.5 \times \text{ULN}$ ALT and/or AST $\geq 3 \times \text{ULN}$ and concurrent TBL $\geq 2 \times \text{ULN}$

**Table C-4. Criteria for Potentially Clinically Important Vital Sign Values**

Vital Sign	Category	Criteria for Potential Clinically Significant Vital Signs
Systolic blood pressure	Low	Value $\leq 90$ mmHg and decrease $\geq 20$ mmHg from Baseline
	High	Value $\geq 160$ mmHg and increase $\geq 20$ mmHg from Baseline
Diastolic blood pressure	Low	Value $\leq 50$ mmHg and decrease $\geq 10$ mmHg from Baseline
	High	Value $\geq 100$ mmHg and increase $\geq 10$ mmHg from Baseline
Pulse	Low	Value $\leq 50$ bpm and decrease $\geq 15$ bpm from Baseline
	High	Value $\geq 120$ bpm and increase $\geq 15$ bpm from Baseline
Weight (adults)	High	$> 7\%$ increase from Baseline
	Low	$> 7\%$ decrease from Baseline
Weight (Adolescents)	Low	$> 7\%$ decrease from Baseline

## Appendix D. Random Seeds

In case of non-convergence, the random seed will be updated by adding 100000 at each attempt until convergence of model happens.

### A. Random Seeds for NRI-MI

Endpoints	Random Seed	
	MCMC procedure	PROC MI
EASI 90 and WP-NRS 0/1 at Week 16 a	1001 for EASI 90; 1002 for WP-NRS	9001 for EASI 90; 9002 for WP-NRS
EASI 90 at Week 16	1003	9003
WP-NRS 0/1 at Week 16 among subjects with Baseline WP-NRS > 1	1004	9004
An improvement (reduction) in WP-NRS $\geq 4$ at Week 16 among subjects with Baseline WP-NRS $\geq 4$ b	1005	9005
WP-NRS 0/1 at Week 4 among subjects with Baseline WP-NRS > 1 c	1006	9006
WP-NRS 0/1 at Week 2 among subjects with Baseline WP-NRS > 1 d	1007	9007
EASI 90 at Week 4 e	1008	9008
EASI 75 at Week 2 a	1009	9009
EASI 100 at Week 16 a	1010	9010
Achievement of 75% reduction in EASI in the head and neck region from Baseline at Week 2, 4, 8, 12, 16	1011	9011
Achievement of 75% reduction in EASI in the trunk region from Baseline at Week 2, 4, 8, 12, 16	1012	9012

Endpoints	Random Seed	
	MCMC procedure	PROC MI
Achievement of 75% reduction in EASI in the upper extremities region from Baseline at Week 2, 4, 8, 12, 16	1013	9013
Achievement of 75% reduction in EASI in the lower extremities region from Baseline at Week 2, 4, 8, 12, 16	1014	9014

Notes:

- The random seed for the corresponding endpoint at the other visits (i.e., Week 2, 4, 8, 12) will use the random seed for that endpoint at Week 16, except EASI 75 where the random seed for this endpoint at the other visits (i.e., Week 4, 8, 12, 16) will use the one at Week 2.
- The random seed for an improvement (reduction) in WP NRS  $\geq 4$  at the other visits (i.e., Week 1, 2, 3, 4, 5, 6, 7, 8, 9, 10, 11, 12, 13, 14 and 15) will use the random seed for this endpoint at Week 16.
- The random seed for WP NRS 0/1 at Week 5, 6, 7, 8, 9, 10, 11, 12, 13, 14 and 15 will use the random seed for this endpoint at Week 4.
- The random seed for WP NRS 0/1 at Week 1 and 3 will use the random seed for this endpoint at Week 2.
- The random seed for EASI 90 at the other visits (i.e., Week 2, 8 and 12) will use the random seed for this endpoint at Week 4.

**B. Random Seed for MI**

Endpoints	Random Seed	
	MCMC procedure	PROC MI
EASI 90 and WP-NRS 0/1 at Week 16	1015 for EASI 90; 1016 for WP-NRS	9015 for EASI 90; 9016 for WP-NRS

**Appendix E. National Cholesterol Education Program (NCEP) Adult Treatment Panel III (ATPIII) for Selected Lipid Parameters**

- LDL cholesterol (< 3.36, ≥ 3.36 and < 4.14, ≥ 4.14 mmol/L)
- HDL cholesterol (< 1.03, ≥ 1.03 mmol/L)
- Total cholesterol (< 5.17, ≥ 5.17 and < 6.21, ≥ 6.21 mmol/L)
- Triglycerides (< 1.69, ≥ 1.69 and < 2.26, ≥ 2.26 mmol/L)

## **Appendix F. Rescue Definition**

The topical and systemic medications for AD therapy are coded to the following drug classes. Among these AD medications, the potential AD rescue medications are determined through a medical review process.

1. Plain Topical Corticosteroids
2. High Potency Topical Corticosteroids
3. Medium Potency Topical Corticosteroids
4. Low Potency Topical Corticosteroids
5. Topical Calcineurin Inhibitor Therapy
6. Other Topical therapy (not including moisturizers/emollients)

Concomitant medications that are categorized as "potential AD rescue" per medical review AND in categories 1 - 6 above are considered as rescue medications in Period 1 and Period 2.

The medical review process is documented in the Rescue Medication Medical Review Process - Upadacitinib AD.

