Investigators should attempt to limit the first step of rescue therapy to topical medications and escalate to systemic medications only for those subjects who do not respond adequately after at least 7 days of topical treatment. Subjects who receive topical rescue treatment during the study treatment period can continue study drug. If a subject needs rescue treatment with a systemic agent (including but not limited to corticosteroids, cyclosporine, methotrexate, mycophenolate mofetil, azathioprine, biologics) or phototherapy, study drug should be permanently discontinued prior to the initiation of rescue systemic agent or phototherapy and subject should be discontinued from the study.

Efficacy and safety assessments should be conducted (e.g., disease severity scores, safety labs) before administering any rescue treatment. An unscheduled visit may be used for this purpose if necessary.

If there are any questions regarding concomitant or prior therapies, the AbbVie TA SD should be contacted who will then discuss it with the AbbVie Therapeutic Area Medical Director (TA MD) and provide a recommendation.

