5.6 Follow-Up After Subject Discontinuation of Study Drug or from Study

Discontinuation of Study Drug

Subjects who prematurely discontinue study drug treatment will be discontinued from study participation entirely.

Following discontinuation of study drug, the subject should be treated in accordance with the investigator's best clinical judgment based on available approved treatment options.

If a subject prematurely discontinues study drug, the procedures outlined for the Premature Discontinuation visit (PD Visit) should be completed as soon as possible, preferably within 2 weeks, and preferably prior to initiation of another therapy. In addition, an End of Treatment Follow-up Visit after the last dose of study drug is required to ensure all treatment-emergent AEs/SAEs have been resolved. The 30-day or 12-week follow-up phone call (for subjects on upadacitinib or dupilumab, respectively) following the last dose of study drug will not be required for any subject who initiates commercially available upadacitinib or dupilumab upon the study Completion Visit or Premature Discontinuation visit. The End of Treatment Follow-up Visit is defined as:

- For subjects on upadacitinib, a 30-day follow-up visit (or phone call if a visit is not possible) after the last study drug dose will be completed to determine the status of any new or ongoing AEs/SAEs and concomitant medications.
- For subjects receiving dupilumab, a 12-week follow-up visit (or phone call if a visit is not possible) after the last study drug injection will be completed to determine the status of any new or ongoing AEs/SAEs and concomitant medications.

For subjects who prematurely discontinued study participation, this visit may be a telephone call if a site visit is not possible.

Premature Discontinuation of Study (Withdrawal of Informed Consent)

If a subject prematurely discontinues study participation (withdrawal of informed consent), the procedures outlined for the Premature Discontinuation visit (PD Visit) should be completed as soon as possible, preferably within 2 weeks, and preferably prior to initiation of another therapy. In addition, if subject is willing, a 30-day or 12 week follow-up phone call or visit after the last dose of study drug (for upadacitinib and dupilumab, respectively) may be completed to ensure all treatment-emergent AEs/SAEs have been resolved.

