## **2.0 Study Objectives and Design**

### **2.1 Study Objectives, Hypotheses and Estimands**

The primary study objective, related to Study Period 1, is to assess the efficacy and safety of upadacitinib, initiated at 15 mg once daily (QD) and dose adjusted based on clinical response, compared with dupilumab as per its label. An additional objective, related to Study Period 2, is to assess the efficacy and safety of upadacitinib, initiated at 15 mg QD and dose adjusted based on clinical response, in subjects with inadequate response to dupilumab and treated at 30 mg QD in subjects with inadequate response to upadacitinib in Period 1. The primary efficacy objective is based on the achievement of an at least 90% reduction in EASI from baseline (EASI 90) and a Worst Pruritus Numerical Rating Scale of 0 or 1 (WP-NRS 0/1) at Week 16 with the treatment of upadacitinib compared with dupilumab in the Intent-to-Treat (ITT) Population, which consists of all randomized

subjects. The secondary efficacy objectives are based on ranked secondary endpoints as defined in Section 3.2 (below) with the treatment of upadacitinib compared with dupilumab in the ITT Population.

The hypothesis corresponding to the primary efficacy endpoint (Section 3.1) is:

The proportion of subjects achieving EASI 90 and WP-NRS 0/1 at Week 16 in those treated with upadacitinib is greater than those treated with dupilumab.

The estimand corresponding to the primary endpoint is defined using the composite variable strategy, as follows:

Difference in the proportion of subjects achieving EASI 90 and WP-NRS 0/1 at Week 16 without the use of rescue medication between upadacitinib and dupilumab in the adolescents and adult subjects with moderate to severe AD who have inadequate response to systemic therapy.

The hypotheses and estimands corresponding to the ranked secondary endpoints are summarized below.

Hypotheses: the proportion of subjects achieving each ranked endpoint in those treated with upadacitinib is greater than those treated with dupilumab.

Estimands: Difference in proportion of subjects achieving each of ranked secondary endpoints without the use of rescue medication between upadacitinib and dupilumab in adolescents and adult subjects with moderate to severe AD who have inadequate response to systemic therapy.

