Baseline, and measurements at each visit in Period 1. The random seed for MCMC and the random seed for PROC MI are specified in [Appendix D](#). The imputed post-baseline measurements will be rounded to the same precision as the observed data before the determination of responder status. WP-NRS 0/1 will be imputed by the same imputation model as EASI 90.

- Step 2: After obtained the EASI 90 and WP-NRS 0/1 (based on weekly average) at Week 16 based on MI imputed values separately, subjects will be characterized as responders or non-responders based on MI imputed datasets. Using the Cochran-Mantel-Haenszel (CMH) model adjusted by main stratification factors (vIGA-AD categories and age), the imputed endpoints will be analyzed using each of the 30 datasets. SAS PROC MIANALYZE will be used to generate the final inferences of the risk difference between upadacitinib and dupilumab. Note that measurements will be considered as missing after the first dose of rescue treatment before MI. Regardless of MI imputed values, subjects after receiving rescue medications will be counted as non-responders.

In Period 2, the primary approach to handle missing data is Observed Cases (OC).

- The OC analysis will not impute values for missing evaluations, and thus a subject who does not have an evaluation at a scheduled visit will not be included in the OC analysis for that visit. The OC analysis will be performed for all variables and will not include values after more than 1 day after discontinuation of study drug.

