  IF 0<=WK16<=0.9*BASE THEN EASI90_16=1;
  ELSE EASI90_16=0;
RUN;

/*****
*/
/* DATA HANDLING STEPS TO MERGE COVID 19 or Other MAR STATUS OMITTED
*/
/* PLACE TO ADD DATA HANDLING AND MERGING STEPS
*/
/*****
*/

/*FOR MI, SKIP THE FOLLOWING CODE, PROCEED TO THE CODE AFTER ANALYSIS
MODEL *//*OVERRIDE MISSING VALUES NOT DUE TO COVID 19 or Other MAR WITH
TRADITIONAL NRI*/
DATA ALLF; SET ALL;
  /*COVID19_XX='Y' IF MISSING AT WEEK XX IS DUE TO COVID 19 or Other
MAR; IF NOT, OVERRIDE WITH TRADITIONAL NRI*/

```

```

    IF COVID19_2 NE 'Y' THEN EASI90_2=EASI90NRI_2;
    IF COVID19_4 NE 'Y' THEN EASI90_4=EASI90NRI_4;
    IF COVID19_8 NE 'Y' THEN EASI90_8=EASI90NRI_8;
    /*VARIABLE EASI90NRI XX: TRADITIONAL NRI DATA AT WEEK XX, WHICH COVERS
    THE SPECIAL HANDLING SUCH AS THE BEFORE AND AFTER EXCEPTION*/
    IF COVID19_12 NE 'Y' THEN EASI90_12=EASI90NRI_12;
    IF COVID19_16 NE 'Y' THEN EASI90_16=EASI90NRI_16;
  RUN;
  PROC SORT DATA=ALLF; BY _IMPUTATION_ SUBJID; RUN;

  /*****/
  /*ANALYSIS MODEL*/
  /*****/

  /*KEY CODE: ANALYZING EACH 'COMPLETE' DATASET*/
  /*****/
  /*COMPARE TREATMENT GROUPS 1 (Dupilumab) AND 2 (Upadacitinib) ONLY*/
  DATA ALL; SET ALL;
    WHERE TRT01PN IN (1,2);
  RUN;

  /*INDIVIDUAL LEVEL DATA > # OF RESPONDERS & # OF SUBJECTS, TO BE READ
  IN TO PROC STDRATE*/
  PROC FREQ DATA=ALL;
    BY IMPUTATION ;
    TABLES TRT01PN*AGEGR1N*VIGAGR1N*EASI90_16/LIST NOCUM NOPRINT
  OUT=COUNT_TABLE;
    /*WEEK 16 RESULTS AS AN EXAMPLE*/
  RUN;
  DATA COUNT_TABLE; SET COUNT_TABLE;
    DROP PERCENT;
  RUN;
  PROC TRANSPOSE DATA=COUNT_TABLE OUT=FREQ_TABLE PREFIX=RESP;
  ID EASI90_16;
  BY IMPUTATION_ TRT01PN AGEGR1N VIGAGR1N;
  VAR COUNT;
  RUN;
  DATA FREQ_TABLE1; SET FREQ_TABLE;
    CASE=RESP1;
    SIZE=SUM(RESP0, RESP1);
    KEEP _IMPUTATION_ TRT01PN AGEGR1N VIGAGR1N CASE SIZE;
  RUN;

  /*RE ORDER TO SET 1 (Dupilumab) AS THE REFERENCE GROUP*/
  DATA FREQ_TABLE2; SET FREQ_TABLE1;
    IF TRT01PN=2 THEN TRT01PN=0;
  RUN;

  /*CALCULATE THE COMMON RISK DIFF FOR EACH COMPLETE DATASET*/

```

```
PROC STDRATE DATA=FREQ TABLE2  
  METHOD=MH STAT=RISK EFFECT=DIFF;  
  BY _IMPUTATION_;  
  POPULATION GROUP=TRT01PN EVENT=CASE TOTAL=SIZE;  
  STRATA AGEGR1N VIGAGR1N / ORDER=DATA STATS (CL=NONE) EFFECT;  
  ODS OUTPUT EFFECT=EFFECT;  
RUN;
```

```
/*COMBINING RESULTS USING PROC MIANALYZE*/  
/*****  
PROC MIANALYZE DATA=EFFECT;  
  ODS OUTPUT PARAMETERESTIMATES=RISK_DIFF_MH;  
  MODELEFFECTS RISKDIFF;  
  STDERR STDERR;  
RUN;
```

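### SAP Appendix F counts only topical drugs as rescue, so the MI sensitivity analysis does not force non-response for subjects given only systemic or phototherapy rescue

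*SAP*

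**What the plan says.** **The analysis definition.** SAP Appendix F opens with "The topical and systemic medications for AD therapy are coded to the following drug classes". It then lists six classes: four of topical corticosteroids, topical calcineurin inhibitors, and other topical therapy. Drugs classed as potential AD rescue "per medical review AND in categories 1 - 6 above are considered as rescue medications in Period 1 and Period 2". Both conditions must be met, so the medical review cannot bring in a drug outside the six classes. Phototherapy has no class.

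**The protocol's use of the word.** Protocol 5.4 asks investigators to try topical drugs first and to escalate after at least 7 days of inadequate response. It continues: "If a subject needs rescue treatment with a systemic agent (including but not limited to corticosteroids, cyclosporine, methotrexate, mycophenolate mofetil, azathioprine, biologics) or phototherapy", then "study drug should be permanently discontinued prior to the initiation of rescue systemic agent or phototherapy", and the subject is to leave the study. Protocol 5.6 repeats the last step: "Subjects who prematurely discontinue study drug treatment will be discontinued from study participation entirely".

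**The estimand.** SAP 2.1 defines response "at Week 16 without the use of rescue medication between upadacitinib and dupilumab". SAP 8.0 and Table 3 make rescue a non-response (composite variable strategy) and handle treatment discontinuation by treatment policy.

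**The missing-data rules.** Under SAP 9.2, NRI-MI and NRI count early withdrawal as non-response. NRI-MI makes an exception for data missing because of COVID-19 or otherwise reasonably MAR. For the MI sensitivity analysis, 9.2 says: "Regardless of MI imputed values, subjects after receiving rescue medications will be counted as non-responders". The sample code in Appendix H 3.0 tells the programmer to bypass the step that overwrites imputed values with NRI: "FOR MI, SKIP THE FOLLOWING CODE, PROCEED TO THE CODE AFTER ANALYSIS".

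**The concern.** A sensitivity analysis of missing data should change the missing-data assumption and leave the estimand alone. Here the MI analysis can also change who counts as rescued. A subject who fails so clearly that systemic rescue is given, without topical rescue first, has no forced non-response in MI. The value is drawn from a model fitted to subjects in follow-up and may come out as a responder. If this happened more often in one arm, the MI difference would shift for a reason unrelated to the assumption being tested.

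The definition may also reach the disposition tables. SAP 5.0 counts rescued subjects in each period. If those rows use Appendix F, systemic-only and phototherapy-only rescue goes uncounted.

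**Working it through.** **1. The plan's own figure.** Protocol 7.9 and SAP 2.4 give 880 subjects at 1:1 (440 per arm), 12% versus 29% (12% + 17 points), two-sided 0.05, and power above 90%. With pooled null variance:

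- mean rate = (0.12 + 0.29)/2 = 0.205
- SE under the null = √(2 × 0.205 × 0.795/440) = 0.0272
- SE under the alternative = √((0.12 × 0.88 + 0.29 × 0.71)/440) = 0.0266
- z = (0.17 − 1.96 × 0.0272)/0.0266 ≈ 4.38, so power = 0.99999

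The stated figure is met. It belongs to the primary comparison, not to the MI analysis.

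**2. Tracing subjects through the three analyses.** The first three rows are subjects with systemic or phototherapy rescue only, before Week 16.

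| Situation at Week 16 | NRI-MI | NRI | MI |
|---|---|---|---|
| Missing, not classed as MAR | non-responder | non-responder | imputed |
| Missing, classed as MAR | imputed | non-responder | imputed |
| In-window value observed after that therapy began | used as observed | used as observed | used as observed |
| Topical rescue used earlier (in Appendix F) | non-responder | non-responder | non-responder |

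The first row is the ordinary case, and only MI departs from the composite strategy there. The exception for subjects who respond both before and after a visit window should not matter, since it needs a later Period 1 assessment. The middle rows are a small residual. Protocol 5.4 asks for efficacy assessments before any rescue, but Protocol 5.6 makes the discontinuation visit only preferably precede other therapy.

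**3. Illustrative size.** The documents give no rate of systemic-only or phototherapy-only rescue, so both inputs are assumptions: f, the share of an arm with only such rescue and a missing Week 16 value; and r, the fraction of them that MI makes responders. Against a full override, the arm's MI response rate rises by f × r. I took r from 0.25 to 1.0 times the planned arm rate (7.25% to 29% on upadacitinib, 3% to 12% on dupilumab).

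| f | Upadacitinib (points) | Dupilumab (points) | Difference (points) |
|---|---|---|---|
| 1% in both arms | 0.07 to 0.29 | 0.03 to 0.12 | +0.04 to +0.17 |
| 5% in both arms | 0.36 to 1.45 | 0.15 to 0.60 | +0.21 to +0.85 |
| 5% upadacitinib only | 0.36 to 1.45 | 0 | +0.36 to +1.45 |
| 5% dupilumab only | 0 | 0.15 to 0.60 | −0.15 to −0.60 |

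The largest entry is 0.05 × 0.29 = 1.45 points, or 440 × 0.05 × 0.29 = 6.4 subjects. It is generous, because it gives failing subjects the full arm rate. The imputation model uses baseline and the Period 1 visits, so a failing history should make r much lower. Even if the planning difference were cut by the largest negative shift, to 12.6% versus 29%, power would still be 0.99998.

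**The case against.** **The design already deals with these subjects.** Topical therapy is the only rescue that can be added while staying on study drug. Anything stronger means leaving the study, which NRI-MI and NRI score as non-response. A topical list is then a fair description of on-study rescue, and the word systemic in the lead-in may be a slip. This largely stands for the primary analysis. It does not cover MI, where leaving the study has no such consequence. If the restriction is deliberate, the SAP does not say so.

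**The intended pathway protects MI too.** Topical treatment comes first, so most subjects who reach systemic rescue will already be flagged. This stands and makes the affected group small. But topical-first is something investigators are asked to attempt, so systemic-only rescue remains possible.

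**Treatment policy covers it.** That strategy uses values collected after discontinuation, and these subjects normally have none. Protocol 7.3 also puts rescue under the composite strategy.

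**Phototherapy is not a medication.** On wording, this limb is weaker, because the estimand speaks of rescue medication. Protocol 5.4 nevertheless groups phototherapy with systemic rescue, and the systemic limb stands without it.

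The separate medical review document is not available. It cannot widen the definition while both conditions are required, but how it records systemic drugs or phototherapy is unknown.

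**Conclusion.** The inconsistency is real and minor. Appendix F is narrower than Protocol 5.4, and in the MI sensitivity analysis this lets some rescued subjects be imputed as responders. Under the assumed inputs the MI difference moves by less than 0.2 to about 1.5 points. The direction depends on which arm has more such subjects. These figures are illustrations, not limits.

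A reader might go further in three ways that the documents do not support:

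- **That the primary result is at risk.** Early withdrawal is already non-response in NRI-MI and NRI. What remains is the in-window value seen after systemic therapy and, in NRI-MI only, data classed as MAR.
- **That every systemic drug started after stopping is rescue.** Protocol 5.6 allows other treatment after discontinuation for any reason, and discontinuation itself falls under treatment policy.
- **That Period 2 is distorted.** Its observed-case analysis drops values more than 1 day after stopping study drug, which largely covers the gap.

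**What to change.** Reconcile Appendix F with Protocol 5.4 in the analysis definition of rescue:

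1. Add the systemic AD drug classes, and phototherapy with a named data source, when medical review judges them given as rescue for AD. Therapy started after stopping study drug for another reason stays under treatment policy.
2. Count these subjects as non-responders from first use in NRI-MI, NRI and MI, and do not class the resulting missing data as MAR.
3. Use the same definition in the SAP 5.0 rescue rows.
4. If records after discontinuation are used to identify rescue, apply the same look-back rule in both arms. Follow-up is 30 days on upadacitinib and 12 weeks on dupilumab (Protocol 5.6), so open-ended capture would differ by arm.

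The cost is wording in Appendix F and SAP 9.2, some re-coding of medication records that Protocol 5.4 already collects, and a source field for phototherapy. MI response rates may be slightly lower. Capture of rescue started after study exit will be incomplete, partly because follow-up contact is waived for subjects who start commercial upadacitinib or dupilumab. No change to patient care is proposed.
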